### 2.1 Primary Objective(s)

2.1.1 Measure the overall response rate for immunotherapy given with quad-shot radiotherapy

### 2.2 Secondary Objective(s)

2.2.1 Measure the response rate at the target lesion.

Quad-Shot Radiotherapy in Combination with Immune Checkpoint Inhibition for  
Advanced/Recurrent Head and Neck Cancer  
Wake Forest Baptist Comprehensive Cancer Center  
WFBCCC60320

- 2.2.2 Measure the response rate at non-target sites *in patients with non-target sites.*
- 2.2.3 Evaluate the durability of response at the target lesion.
- 2.2.4 Evaluate progression-free survival.
- 2.2.5 Evaluate overall survival.
- 2.2.6 Assess the tolerability of the combination of quad-shot radiotherapy with immunotherapy in order to assess the feasibility of this treatment regimen.

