The study treatment portion ends for all patients with the last administration of the immunotherapy.

We will monitor and document clinical toxicity per NCI Common Terminology Criteria for Adverse Events version 5.0 during the treatment and for two additional visits 30 days apart from the end of treatment with immunotherapy. Subjects who decline to return to the site for evaluations will be offered follow-up by phone up to 2 months as an alternative and the PI will make every effort to collect toxicity data from medical records.

Patients will be subsequently followed for progression-free survival and overall survival outcomes. Subsequent visits can be accomplished in person or over the phone and clinical and imaging data will be collected from medical records as available.

Patient-reported outcomes will be obtained at each time point using a tailored checklist of PRO-CTCAE head and neck cancer-specific items.

Saliva and blood for correlative studies will be collected before each treatment with immunotherapy for the first 5 administrations and before the quad-shot administration. Saliva and blood samples will only need to be collected on the first day of Quadshot treatment. In the cases in which the patients will receive a 2nd quad-shot and possibly a third quad-shot, blood and saliva will be collected before the respective radiation treatments as well as before the immunotherapy cycles that proceed and follow the quad-shot treatments.

PD-L1 receptors will be tested in all patients as per standard of care. Next generation sequencing is encouraged and will be done whenever possible from the blood or tumor if available.

Quad-Shot Radiotherapy in Combination with Immune Checkpoint Inhibition for  
Advanced/Recurrent Head and Neck Cancer  
Wake Forest Baptist Comprehensive Cancer Center  
WFBCCC60320

If any patient does not complete the study treatment and investigations, the patient will be replaced.

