#### **5.2 Secondary Outcomes**

- 5.2.1 The response rate in the target lesion measured according to RECIST 1.1 (Section 7.1.3).
- 5.2.2 The response rate in the non-target lesions (if applicable) will be measured according to RECIST 1.1 (Section 7.1.3).
- 5.2.3 The duration of response at the target lesion will be defined as the duration from the time measurement criteria are met for CR or PR (whichever is first recorded) until the first date of recurrent or progressive disease as defined in Section 7.1.4.

Quad-Shot Radiotherapy in Combination with Immune Checkpoint Inhibition for  
Advanced/Recurrent Head and Neck Cancer  
Wake Forest Baptist Comprehensive Cancer Center  
WFBCCC60320

- 5.2.4 Progression-free survival (PFS) will be defined as in Section 7.1.5.
- 5.2.5 Overall survival (OS) will be defined as in Section 7.1.5.
- 5.2.6 Tolerability will be measured using the Patient-Reported Outcomes version of the Common Terminology Criteria for Adverse Events (PRO-CTCAE).

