### **6.6 Criteria for Removal from Study**

Patients will be removed from study when any of the following criteria apply:

Quad-Shot Radiotherapy in Combination with Immune Checkpoint Inhibition for Advanced/Recurrent Head and Neck Cancer  
Wake Forest Baptist Comprehensive Cancer Center  
WFBCCC60320

- Patient withdrawal of consent or loss to follow-up.
- Adverse event that, in the opinion of the investigator or the sponsor, contraindicates further dosing.
- Subject is determined to have met one or more of the exclusion criteria for study participation at study entry and continuing investigational therapy might constitute a safety risk.
- Pregnancy or intent to become pregnant
- Grade  $\geq 3$  infusion reaction.
- Subject noncompliance that, in the opinion of the investigator or sponsor, warrants withdrawal; eg, refusal to adhere to scheduled visits.
- Initiation of alternative anticancer therapy including another investigational agent.
- Confirmation of PD and investigator determination that the subject is no longer benefiting from protocol treatment.
- Death.

Subjects who are permanently discontinued from further receipt of investigational product, regardless of the reason (withdrawal of consent, due to an AE, other), will be identified as having permanently discontinued treatment.

Subjects who are removed from study prior to completing at least 2 cycles of ICI followed by at least 1 cycle of quad-shot radiotherapy followed by at least 2 cycles of ICI will be discontinued from the study and replaced.

Subjects who are permanently discontinued from receiving investigational product will be followed for safety until follow-up criteria are met in Section 6.4. Subjects who decline to return to the site for evaluations will be offered follow-up by phone for at least 60 days as an alternative.

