### 7.1.1 Definitions

- **Evaluable for toxicity:**

Only those patients who have received at least 1 fraction of radiotherapy and at least 1 cycle of ICI will be evaluable for toxicity from the time of their first fraction of radiotherapy.

- **Evaluable for objective response:**

Only those patients who received at least one cycle of quad-shot radiotherapy (given after at least 2 cycles of ICI), and have had their target disease re-evaluated will be evaluable. These patients will have their response classified according to the definitions stated below.

Note: Per Section 6.6, subjects who are removed from study prior to completing at least 2 cycles of ICI followed by at least 1 cycle of quad-shot radiotherapy followed by at least 2 cycles of ICI will be discontinued from the study and replaced.

- **Evaluable Non-Target Disease Response.**

Patients who have lesions present at baseline that are evaluable but do not meet the definitions of target disease, have received at least one cycle of quad-shot radiotherapy, and have had their disease re-evaluated will be considered evaluable for non-target disease. The response assessment is based on the presence, absence, or unequivocal progression of the lesions.

- **Measurable disease / measurable lesions**

Measurable lesions are defined as those that can be accurately measured in at least one dimension (longest diameter to be recorded) as  $\geq 20$  mm by chest x-ray, as  $\geq 10$  mm with CT scan, or  $\geq 10$  mm with calipers by clinical exam. All tumor measurements must be recorded in millimeters (or decimal fractions of centimeters).

- **Malignant lymph nodes.**

To be considered pathologically enlarged and measurable, a lymph node must be  $\geq 15$  mm in short axis when assessed by CT scan (CT scan slice thickness recommended to be no greater than 5 mm). At baseline and in follow-up, only the short axis will be measured and followed.

- **Non-measurable disease / non-measurable lesions:**

All other lesions (or sites of disease), including small lesions (longest diameter  $<10$  mm or pathological lymph nodes with  $\geq 10$  to  $<15$  mm short axis), are considered non-measurable disease. Bone lesions, leptomeningeal disease, ascites, pleural/pericardial effusions, lymphangitis cutis/pneumonitis, inflammatory breast disease, and abdominal masses (not followed by CT or MRI), are considered as non-measurable.

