### **8.3 STRC SAE Reporting Requirements**

The Data Safety Monitoring Committee (DSMC) is responsible for reviewing SAEs for WFBCCC Institutional studies as outlined in Appendix B. All Adverse Events that occur during protocol intervention and are coded as either 1) unexpected grade 4, 2) unplanned inpatient hospitalization  $\geq$  24 hours (regardless of grade), or grade 5 (death) must be reported to the DSMC using the SAE console in WISER.

All WFBCCC Clinical Protocol and Data Management (CPDM) staff members assisting a Principal Investigator in investigating, documenting and reporting an SAE qualifying for DSMC reporting are responsible for informing a clinical member of the DSMC as well as the entire committee via the email notification procedure of the occurrence of an SAE.

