### 11.2 Analysis of Secondary Objective

There are 6 secondary outcomes of interest for this pilot study. These are 1) response rate for the target lesion; 2) response rate for non-target lesions 3) duration of response for the target lesion 4) progression free survival (PFS) 5) overall survival (OS) and tolerability assessed using PRO-CTCAE. We now describe our analytic approach for each measure.

For the response rate measures we will estimate the percent of responders (PR or CR) and the corresponding 95% Clopper Pearson exact confidence intervals. For the duration of response, among responders we will estimate both the mean and median duration and the corresponding 95% confidence intervals for the mean and inter-quartile range for the median. For time to event measures (PFS and OS) we will estimate Kaplan Meier survival curves and estimate the median time to event times as well as the percent PFS and OS at 6 months and 1 year post treatment. For tolerability, we will estimate the percent of patients with different AEs assessed using the PRO-CTCAE and corresponding 95% Clopper Pearson exact confidence intervals.

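### Tolerability rests on PRO-CTCAE alone and toxicity is counted only from the first radiotherapy fraction, so clinician-graded events enter no stated outcome, and lead-in events and dropouts enter no stated safety or feasibility result

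*Combined protocol and SAP*

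**What the plan says.** - **Objective.** Section 2.2.6 reads "Assess the tolerability of the combination of quad-shot radiotherapy with immunotherapy in order to assess the feasibility of this treatment regimen". Section 2.0 makes feasibility part of the study hypothesis.
- **Measure and analysis.** Section 5.2.6 states "Tolerability will be measured using the Patient-Reported Outcomes version of the Common Terminology Criteria for Adverse Events (PRO-CTCAE". The matching analysis in Section 11.2 is that "we will estimate the percent of patients with different AEs assessed using the PRO-CTCAE", with exact 95% intervals. Section 11 contains no estimate of CTCAE grade, immune-related events, treatment-ending events or completion.
- **Collection.** Section 4.2 says "We will monitor and document clinical toxicity per NCI Common Terminology Criteria for Adverse Events version 5.0 during the treatment" and at two later visits. Section 13.2 lists an adverse event log. Under Section 8.3, unexpected grade 4 events, unplanned hospitalisations and deaths "must be reported to the DSMC using the SAE console in WISER".
- **Toxicity population.** Under Section 7.1.1, only patients with at least one radiotherapy fraction and one cycle of pembrolizumab (the immune checkpoint inhibitor, ICI) "will be evaluable for toxicity from the time of their first fraction of radiotherapy".
- **Replacement.** Section 4.2 says "If any patient does not complete the study treatment and investigations, the patient will be replaced". Section 6.6 is narrower. It begins "Subjects who are removed from study prior to completing at least 2 cycles of ICI" and goes on to require a quad-shot cycle and two further ICI cycles; patients who fall short are discontinued and replaced.

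**The concern.** Two separate rules act on the same objective.

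The first is the choice of instrument. The special-interest list in Section 8.1 includes liver enzyme rises, nephritis, endocrinopathy and raised lipase or amylase. These are found by laboratory tests or clinical diagnosis, and a patient symptom checklist cannot grade them. The introduction itself cites concern about increased radiation and immune-mediated effects as the reason for avoiding same-day treatment. Clinician-graded events of that kind could follow radiotherapy and still appear in no stated outcome.

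The second is conditioning. The regimen begins with two or three ICI cycles before radiotherapy. Starting the toxicity count at the first fraction and replacing early stoppers makes the toxicity population consist of patients who got through the lead-in. For feasibility, the patients who did not get through are the main evidence. A pilot meant to inform later studies could report good tolerability without ever stating how many patients had to start for 15 to finish.

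**Working it through.** **1. The plan's own figure.** Section 11.3 gives a maximum 95% Clopper-Pearson width of 0.52 with n = 15, at 7/15. The limits are:

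- lower = Beta quantile(0.025; x, n − x + 1)
- upper = Beta quantile(0.975; x + 1, n − x)

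For x = 7 and n = 15 they are 0.2127 and 0.7341, a width of 0.5214, or about ±0.26. The stated figure reproduces, so no published number is in error here. The same method is used below.

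**2. Exposure before the toxicity count starts.** ICI cycles last 3 weeks. Section 4.2 places the first quad-shot in the last week of cycle 2 or cycle 3. The last week of cycle 2 runs from week 5 to week 6, and that of cycle 3 from week 8 to week 9. About 5 to 9 weeks of pembrolizumab exposure therefore precede the first fraction. (Section 4.3.3 names only the slot between cycles 2 and 3, while Sections 4.2 and 4.3.6 allow either; these passages need reconciling.)

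**3. Where each kind of information goes.**

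| Information | Collected | Stated safety or feasibility result |
|---|---|---|
| PRO-CTCAE symptoms | Yes, including ICI cycles 1-3 (Section 6.1) | Yes (11.2), denominator not stated |
| CTCAE events from the first fraction | Yes | None |
| CTCAE events before the first fraction | Yes | None, and outside the toxicity period of 7.1.1 |
| Stopping before the required sequence | Yes (off-treatment and off-study forms, 13.2) | None; patient replaced |

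One group falls between rules. A patient with one fraction who stops before two further ICI cycles is toxicity-evaluable under 7.1.1 but discontinued and replaced under 6.6. The plan does not say whether that patient stays in the tolerability denominator.

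**4. Size of the missing completion rate.** The documents give no early-loss rate, so d is assumed from 10% to 40%. Here early loss means stopping before 2 ICI cycles, quad-shot and 2 ICI cycles are complete, and the 15 evaluable patients are taken to be those who finish that sequence. Starters N = 15/(1 − d), rounded up; replaced = N − 15; completion = 15/N.

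| Assumed d | 15/(1 − d) | N | Replaced | Completion | 95% interval |
|---|---|---|---|---|---|
| 10% | 16.7 | 17 | 2 | 88% | 64-99% |
| 20% | 18.75 | 19 | 4 | 79% | 54-94% |
| 30% | 21.4 | 22 | 7 | 68% | 45-86% |
| 40% | 25 | 25 | 10 | 60% | 39-79% |

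**5. Effect on a severe-event rate (illustration only).** Suppose 1 of the 15 evaluable patients has a severe event: 1/15 = 6.7% (0.2-32%). Suppose also that 20% are lost and, as an extreme case, all 4 stopped in the lead-in with a severe event. Over everyone treated the rate is (1 + 4)/(15 + 4) = 5/19 = 26% (9-51%). Neither input comes from the documents.

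**The case against.** The strongest defence is that objective 2.2.6 concerns the combination, and the combination exists only from the first fraction. Pembrolizumab alone is standard care that these patients were already due to receive. For combination toxicity, starting the count at radiotherapy is a coherent choice. That stands, and the from-first-fraction view should be kept. It does not explain why clinician-graded events after radiotherapy also enter no outcome, and it does not serve feasibility, which covers the whole sequence.

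Four stronger readings are tempting, but the documents do not support them:

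- **Early stoppers vanish from every analysis, and death belongs to no outcome.** Death is the OS event and one of the PFS events. Section 7.1.5 runs both from registration, and no stated rule excludes lead-in dropouts from them.
- **Replacement means the data are discarded.** Replacement secures 15 evaluable patients. Section 6.6 still requires safety follow-up after discontinuation, and Appendix D requires all adverse events in enrolled patients to be entered in WISER.
- **Lead-in symptom reports are certainly excluded.** Section 11.2 neither cites 7.1.1 nor names a denominator, so for PRO-CTCAE the point is ambiguous.
- **About 4 of 15 patients would have uncounted serious events.** This multiplies the 28% serious-reaction figure in Section 8.1 by 15 (0.28 × 15 = 4.2). That figure has no stated population or exposure period and is not a lead-in rate, and the 15 are patients who did reach radiotherapy. The 5% permanent-discontinuation figure beside it (0.05 × 15 = 0.75) has no stated population or period either.

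Case-level oversight is also intact, since the DSMC reviews reported events and can suspend the trial.

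**Conclusion.** The point holds as a gap in outcome definition and analysis, not in data collection or safety oversight. Tolerability has one stated measure and one stated analysis, both patient-reported. Clinician-graded grade 3 or higher, immune-related, laboratory-based and treatment-ending events have no stated place in the results. The toxicity-evaluable and replacement rules leave lead-in events and dropouts outside any stated safety or feasibility result, except that deaths and progression may enter OS and PFS.

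This is more than an omitted table: clinician-graded tables added under 7.1.1 as written would still cover only patients who reached radiotherapy, and only from that point. The size depends wholly on an early-loss rate the documents do not give. Over an assumed 10% to 40%, 2 to 10 patients would be replaced and completion would run from 88% down to 60%. The change should be made before analysis.

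**What to change.** Amend Sections 5.2.6, 7.1.1 and 11.2 as follows.

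1. Keep PRO-CTCAE as a tolerability measure, state its denominator, and keep the from-first-fraction view of combination toxicity.
2. Add a safety set of all patients given any pembrolizumab. In it, report with Clopper-Pearson intervals the percent with a CTCAE v5.0 event of grade 3 or higher, the percent with an immune-related event, and the percent with an event ending treatment. Split each into before and from the first fraction.
3. Report as the feasibility result, with its exact interval, the percent of all registered patients who complete 2 ICI cycles, quad-shot, then 2 ICI cycles.
4. State that replaced patients stay in the denominators of items 2 and 3. This also settles the patient who has had a fraction and is then replaced.

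The cost is wording and a few more tables from data already collected, with no added visits or patients. The downside is that reported tolerability is likely to look less favourable than under the current rules.

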### **5.3 Exploratory Objectives**

Blood will be utilized to measure the effect of immunotherapy alone as well as in combination with quad-shot therapy on increase of the circulating immune microRNA.

In addition, blood and saliva specimens will be utilized for mechanistic investigations of the effects of quad-shot on the response to immune checkpoint inhibitors. Detailed and comprehensive single cell RNA sequencing and multi-omics analysis of both plasma and exosomes fractions will be performed.

Saliva will be utilized for metabolomics and miRNA and RNAseq analysis of oral microbiome

Quad-Shot Radiotherapy in Combination with Immune Checkpoint Inhibition for Advanced/Recurrent Head and Neck Cancer  
 Wake Forest Baptist Comprehensive Cancer Center  
 WFBCCC60320

## 6.0 Treatment Plan

### 6.1 Study Calendar

	Screening/ Pre- Registration i	Cycle 1-3 ICI	QuadShot #1	Cycles 4-6 ICI	QuadShot #2	Cycles 7-11 ICI	Quadshot #3	Maintenance ICI Every 3 Weeks
Initial Screening for Eligibility	X							
Informed Consent	X							
Demographics	X							
Medical and Surgical History	X							
Medication List	X							
Comorbidities	X							
Tobacco Use History	X							
Pre-Toxicity Form	X							
Hepatitis A antibody Hepatitis B surface Ag, Hepatitis C antibody and HIV	X							
Urine hCG or serum $\beta$ hCG a	X	As clinically indicated						
Pembrolizumab Administration		X		X		X		X
Quad-shot Radiotherapy h			X		X		X	
Physical Examination b	X	X		X		X		X
Vital Signs	X	X c		X		X		X

Quad-Shot Radiotherapy in Combination with Immune Checkpoint Inhibition for Advanced/Recurrent Head and Neck Cancer  
 Wake Forest Baptist Comprehensive Cancer Center  
 WFBCCC60320

Electrocardiogram d	X	X	As clinically indicated				
Concomitant Medications	X	X		X		X	
Adverse event/serious adverse event assessment				X		X	
ECOG Performance Status	X	X	X m	X	X m		X m
Liver enzyme panel	X	X i		X		X	X
Serum Chemistry	X	X i		X		X	X
Magnesium	X		As clinically indicated				
Uric Acid	X		As clinically indicated				
LDH	X	X i	As clinically indicated				
Amylase, Lipase	X	X i		X		X	X
Thyroid function tests (TSH and fT3 and fT4) e	X	X i		X		X	X
Hematology	X	X i		X		X	X
Urinalysis	X		As clinically indicated				
Coagulation parameters	X		As clinically indicated				
Tumor Assessment with CT scan or MRI f	X		X		X		X
Tumor assessment with PET scan g	X		X		X		X
Blood Collection for Correlatives		X	X	X k	X k	X k	X k
Saliva Collection for Correlatives		X	X	X k	X k	X k	X k
PRO-CTCAE QOL Questionnaire h		X		X		X	X

Quad-Shot Radiotherapy in Combination with Immune Checkpoint Inhibition for Advanced/Recurrent Head and Neck Cancer  
Wake Forest Baptist Comprehensive Cancer Center  
WFBCCC60320

- a. Female subjects of childbearing potential only
- b. Full physical examination at baseline; targeted physical examination at other timepoints
- c. With first administration of pembrolizumab only and then as clinically indicated. Subjects will have their blood pressure and pulse measured before, during and after the infusion at the following times (based on a 60-minute infusion):
  - At the beginning of the infusion (at 0 minutes)
  - At 30 minutes during the infusion ( $\pm 5$  minutes)
  - At the end of the infusion (at 60 minutes  $\pm 5$  minutes)
  - In the 1 hour observation period post-infusion: 30 and 60 minutes after the infusion (ie, 90 and 120 minutes from the start of the infusion) ( $\pm 5$  minutes) – for the first infusion only and then for subsequent infusions as clinically indicated
  - If the infusion takes longer than 60 minutes then blood pressure and pulse measurements should be collected every 30 minutes ( $\pm 5$  minutes) and as described above or more frequently if clinically indicated.
- d. ECG during screening and at Day1 –baseline. Thereafter as clinically indicated. Baseline and abnormal ECG at any time in triplicate others single. Triplicate EKG is only needed at screening, and not on Cycle 1 Day 1 unless something clinically significant was seen at screening.
- e. Free T3 and free T4 will only be measured if TSH is abnormal. They should also be measured if there is clinical suspicion of an adverse event related to the endocrine system.
- f. CT (preferred) or MRI scans, preferably with IV contrast, are collected during screening (for baseline) and as close to and prior to initiation of study treatment but not more than 14 days  $\pm$  5 days prior to first treatment. Will then be performed every 5 cycles ( $\pm$  1 cycle) for tumor response measurement
- g. PET scan will be performed in all cases if reimbursed by Medical Insurance or funded. It will be performed as close to the initiation of treatment but not more than 28 days prior to treatment. Will then be performed in follow up as clinically indicated and if approved by medical insurance.
- h. Prior to cycle 4 (between pembrolizumab cycle 2-3 or 3-4) for all patients. Subsequent quad-shot cycles, if applicable, will be given as follows: quad-shot cycle #2: prior to cycle 8 (between pembrolizumab cycles 6-7 or 7-8); quad-shot cycle #3: prior to cycle 13 (between pembrolizumab cycles 11-12 or 12-13). Radiotherapy shall not be given on the same day as immunotherapy administration. Though specific days are not mandated, it is recommended that at least 1 day of each quad-shot cycle is given within 7 days of the upcoming ICI administration. Only one quad-shot cycle is mandated by the protocol; the 2nd and 3rd cycles may be completed at the discretion of the treating radiation oncologist as per Section 4.3.
- i. Pre-study requirements listed in table must be completed **within** 30 days prior to registration.
- j. If screening laboratory assessments are performed within 3 days prior to Day 1 they do not need to be repeated at Day 1. Results for safety bloods must be available and reviewed before commencing an infusion. Creatinine clearance, gamma glutamyltransferase, magnesium, and uric acid testing are to be performed at screening, on Day 1 (unless screening laboratory assessments are performed within 3 days prior to Day 1), and if clinically indicated.
- k. Blood and Saliva for correlatives will be collected before each of the first five cycles of immunotherapy and before the first quad-shot treatment. Saliva and blood samples will only need to be collected on the first day of Quadshot treatment. For patients treated with subsequent radiotherapy cycles (between ICI cycles 6-7 or 7-8  $\pm$  cycles 11-12 or 12-13) to be collected before the quad-shot treatment and before each ICI cycle administered before and after the quad-shot treatment (ICI cycles 6 and 7 or cycles 7 and 8  $\pm$  before cycles 11 and 12 or 12 and 13)
- l. The PRO-CTCAE
- m. ECOG performance status needs to be collected only on one of the two days of quadshot treatment – either day 1 or day 2.

